Screening Visit, Part II (about 2 hours) will be conducted in LSU Exercise Physiology Laboratory and will include height, weight, the completion of the International Physical Activity Questionnaire-Elderly,¹⁹ Sedentary Behavior Questionnaire,²⁰ and PROMIS Physical Function Questionnaire^{21, 22}, and the Pittsburgh Fatigability Questionnaire. We will also measure height and weight. We will measure isokinetic strength and endurance of the knee extensors (Biodek System 3) and the 1-repetition maximums (1-RMs)

for the knee extension, leg press, and chest press. Note: the 1-RM measurements may be performed prior to your regularly scheduled exercise session during the first and last week of the intervention. We will also measure grip strength using a hand dynamometer.

Baseline Physical Activity Monitoring. At the end of part II of the screening visit, all subjects who are deemed eligible to continue onto the pre-training visits described below will be provided two devices to measure their physical activity leading up to their pre-intervention testing. A wrist-worn physical activity monitor (Actigraph, GT9X) will be issued to the subjects to wear 24-h/d for 7-days (± 3 days) prior to their pre-training visits to quantify objectively their PA and ST. Subjects will also be asked to wear a second physical activity monitor (Actigraph, GT9X) on their thigh 24-h/d for 7-days (± 3 days). Subjects will be asked to return their physical activity monitors during the Pre-training Visit 1 (V1). In the event that a subject is deemed ineligible after part II of the screening visit, we would request that the subject return his/her physical activity monitors at their earliest convenience. We will screen raw data from these monitors for periods of valid wear-time with a required minimum wear-time of 10 h per valid wear-day and 4 valid wear-days per week.^{23, 24} We will use standard algorithms to characterize the patterns of PA and ST.²⁵

Baseline Dietary Record. Subjects will be asked to record their dietary intake for the 24 hrs prior to their pretraining visit 1. They also will be asked to replicate their dietary intake before posttraining visit 4. Moreover, they will be asked to refrain from consuming caffeine or participating in vigorous exercise 48 hours prior to these visits.

Pre-training Visits 1 (V1). (About 5 hours). V1 will be scheduled at least 7 days after screening visit Part II.

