Exercise Interventions. After completing V2, we will randomize the subjects to one of three 16-week interventions: (i) RE, (ii) REALPA breaks in ST, or (iii) RE+AE (**Figure 3**). The RE+AE group serves as the standard of care. The RE group will complete supervised RE (2 x/wk). The REALPA breaks in ST group will complete a supervised RE (2 x/wk) and regular unsupervised LPA breaks in ST (5 d/wk, 6x10 min breaks/d at 2 METS (~30-40% VO_2 peak), ~500 kcal/wk above resting metabolism). The RE+AE group will complete supervised RE (2 x/wk) and calorically matched moderate intensity AE (3 d/wk, 50 min/session at 4 METS (~60-75% VO_2 peak), ~500 kcal/week above resting metabolism). The RE component for all 3 groups will consist of 3 sets of 10-12 repetitions to failure for a total of 8 exercises targeting the large muscle groups (**Table 2**). The AE component for the RE+AE group will consist of treadmill walking at ~4 METs for 50 min

(Table 2). The RE and AE sessions will take place in LSU School of Kinesiology's Exercise Training Facility under direct supervision (Drs. [name], [name], and [name] with the assistance of trained graduate students). All supervised exercise sessions will include a 5 minute warm-up and cool-down on either a bike or treadmill. We will provide subjects flexibility on the days per week that they can complete their exercise sessions. Note: The start of the exercise intervention will be at least 5 days post V2 to allow for adequate recovery from the muscle biopsy, but no more than 6 weeks after V2. Up to 2 weeks may be added to a subjects exercise intervention, to allow for potential make-up of missed exercise sessions and to provide flexibility for scheduling study visits.

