One-Repetition Maximum Testing (About 15 minutes). Skeletal muscle strength will be assessed using a 1-RM measurements obtained for the leg extension, leg press, and chest press. Subjects will be provided a dynamic warm-up consisting of weight they can lift at least 6 times. Subjects will then complete about 4-6 trials to reach the maximum weight they can lift one time. Subjects will start the first trial at relatively low weight, followed by 2 to 3 min rest. Each subsequent attempt, the weight the subjects lift will increase until your 1-RM is achieved. **Note:** these measurements may be performed prior to a regularly scheduled exercise session during each subject's first and last week of the intervention. In some subjects, we may use a submaximal test (e.g., 3 RM) to estimate their 1RM.

Handgrip Strength Testing (about 5 minutes). Handgrip strength will be measured with a hand dynamometer. This test involves squeezing on the hand grip dynamometer as hard as you can for several seconds. This assessment will be repeated 2-3 times per hand.

Body Composition Assessments at LSU (about 10 minutes). The following body composition assessments will take place in the LSU Exercise Physiology Laboratory during V1 and V4).

Bioelectrical Impedance Analysis (BIA) - LSU (about 5 minutes) The BIA test will measure the amount of total body water, fat free mass, and fat mass in the body. The subject will be asked to remove all footwear and socks/stockings. Once changed and barefoot, the subject will be asked to stand on a scale

(similar to a large gym scale) and to hold on to hand electrodes on each side of the scale. The subject will be asked to step off of the scale once the measurement is complete (less than one minute).

Body Composition Assessments at PBRC (about 30 minutes). The following body composition assessments will take place in [name] Laboratory during V2 and V5.

Circumferences (about 10 minutes). Circumferences of the waist, hip, upper arms and thighs will be measured using the National Health and Nutrition Examination Survey (NHANES) protocol. Measurements will be made by a trained study personnel using a calibrated tape measure. We have a circumference training and validation program in place from earlier studies.

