[name] (LSU) and [name] (PBRC). We will screen all data for distributional properties (mean, median, range) and departures from normality prior to substantive analyses. To test the main effects of time, treatment, and their interaction on the primary outcomes, we will use mixed-effects two-way Analysis of Variance (ANOVA) models ($\alpha=0.05$). The models will include parameters to estimate the main effects of time (pre- and post-training) and treatment (RE, REALPA breaks in ST, RE+AE) on the dependent variables. We will use *Fisher's Least Significant Differences test* to examine within and between group mean differences ($\alpha=0.05$). We will test all models for the main effect of sex. If the main effect of sex is significant, we will perform additional exploratory analyses stratified by sex. Other covariates that may be included in the models include race, change in body weight, and baseline SPPB scores. We will also compare adherence rates across the study groups.

Sample Size, Power Analysis and Randomization. We will use the data collected in this **pilot study** to estimate effect sizes for the primary and secondary outcomes, which we will use to inform our power analyses for a follow-up R01 application designed to test the efficacy of our novel exercise intervention on skeletal muscle and cardiometabolic health in sedentary older adults. We will use a fixed sample size of 12 subjects per group, because increasing the sample size above 12 (i.e., 12 to 15) has diminishing benefit in estimations effect sizes and 95% confidence intervals often referred to as the “rule of 12”.^{39, 40} Thus, we will recruit up to 15 subjects per group to account for a 20% attrition rate. The NIH’s Clinical and Translational Science Awards Biostatistics, Epidemiology, and Research Design (BERD) units recommend 12 subjects per group for estimating effect sizes and 95% confidence intervals.³⁹ Following baseline testing, we will randomize the study subjects to one of the three interventions using a randomized, permuted, block design stratified by sex and race.

PROVISIONS TO MONITOR THE DATA TO ENSURE THE SAFETY OF SUBJECTS

This Human Subjects Research meets the definition of a Clinical Trial. This study does not involve major risk to subjects. Efforts to minimize the potential risks of the assessment methods and outcome variables include frequent monitoring by the investigators to assure that no volunteer suffers any adverse effects from participating in the research.

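### Baseline 1-RM may be measured in week 1 of the intervention, after randomisation and biopsy, so it need not be a pre-treatment value

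*Combined protocol and SAP*

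**What the plan says.** The section on Screening Visit, Part II places the baseline 1-RM at that visit, together with the isokinetic and grip tests. It then adds a note: "the 1-RM measurements may be performed prior to your regularly scheduled exercise session during the first and last week of the intervention". One-Repetition Maximum Testing, in the detailed methods, gives the same permission: "these measurements may be performed prior to a regularly scheduled exercise session during each subject's first and last week of the intervention". Neither note says that a first-week test must precede the first session.

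The muscle biopsy of the vastus lateralis is at V2. On allocation, Exercise Interventions says "After completing V2, we will randomize the subjects to one of three 16-week interventions". On the start of training it says "The start of the exercise intervention will be at least 5 days post V2", with an upper limit of 6 weeks. Sample Size, Power Analysis and Randomization gives the intended order: "Following baseline testing, we will randomize the study subjects to one of the three interventions".

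On method, One-Repetition Maximum Testing adds: "In some subjects, we may use a submaximal test (e.g., 3 RM) to estimate their 1RM". It does not say whether a subject tested that way at baseline is tested the same way at the end.

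**The concern.** A baseline should be fixed before allocation is known and before treatment starts. A first-week 1-RM fails the first condition every time and may fail the second. The analysis model has a time factor with only two levels, before and after training, so a screening value and a first-week value would be pooled as the same thing. No rule says which subjects use the option, and nothing requires equal use across arms.

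The shift could go either way. Soreness after the biopsy or an early session would lower the baseline and enlarge the apparent gain. Practice or early training would raise it and shrink the gain. The assigned activity that may come first also differs by arm. The documents describe no masking of the staff who test, so the tester may know the arm when the baseline is taken and when the choice between a true and a submaximal test is made. The biopsy is not placed symmetrically either: a first-week test follows the V2 biopsy, whereas the post-training test at V3 precedes the one at V5.

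At stake is the interpretation of 1-RM change, within and between arms.

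**Working it through.** The plan gives no figure for this point, so the check is one of sequence and exposure, followed by an illustration on stated assumptions.

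**1. Sequence.** Screening Part II; V1 at least 7 days later; V2 with biopsy at least 24 hours and at most 2 weeks after V1; randomisation; training from 5 days to 6 weeks after V2.
- Shortest gap from Screening Part II to the start of training: 7 + 1 + 5 = 13 days.
- With V1 on day 7 and the later intervals at their limits: 7 + 14 + 42 = 63 days, or 9 weeks. V1 has no stated upper limit, so the gap can be longer.

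The two permitted baseline dates are therefore about two weeks apart at the least. The later one always falls after randomisation and biopsy.

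**2. Exposure before a first-week test.** Counting Table 2 activities on days before the session in question:

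| Arm | Tested before | Already done |
|---|---|---|
| RE | Tue | none |
| RE | Thu | 1 RE |
| REALPA | Tue | 1 LPA day |
| REALPA | Thu | 1 RE + 3 LPA days (3 × 6 = 18 bouts) |
| RE+AE | Mon | none |
| RE+AE | Tue | 1 AE |
| RE+AE | Wed | 1 RE + 1 AE |
| RE+AE | Thu | 1 RE + 2 AE |
| RE+AE | Fri | 2 RE + 2 AE |

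Subjects may vary their training days, so this calendar is an example.

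**3. How much training that is.** RE sessions in total: 2 × 16 = 32. At most 1/32 = 3.1% (RE, REALPA) or 2/32 = 6.3% (RE+AE) can precede the test, and these fall in the month when the load is still being built up.

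**4. Illustrative size.** Every input here is an assumption; the documents supply none of them.
- *Early gain.* If a share f of an arm is tested late and a share g of the 16-week gain has already occurred, the change is understated by f × g: from 0.25 × 0.05 = 1.25% to 1.00 × 0.20 = 20%.
- *Soreness.* With a true gain of 20% and a baseline lowered by 5% or 10%, the apparent gain is 1.20/0.95 − 1 = 26.3% or 1.20/0.90 − 1 = 33.3%. That is 6.3 or 13.3 points too high in those tested late, and 3.2 or 6.7 points in the arm mean if half are.
- *Between arms.* If use of the option differs by 25% to 100% of subjects and the baseline shift is 0.05 to 0.30 SD, the bias is 0.25 × 0.05 = 0.01 SD to 1.00 × 0.30 = 0.30 SD. Equal use with shifts differing by the same amounts gives the same range.

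As a yardstick, 12 completers per arm (the plan's rule-of-thumb size; 12/(1 − 0.20) = 15 recruited, as stated) give 80% power at two-sided 0.05 for (1.960 + 0.842) × √(2/12) = 1.14 SD.

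**The case against.** The strongest reply concerns reach. The primary strength measure is isokinetic dynamometry, and the Aim 1 secondary outcomes are muscle OXPHOS and oxidative damage to muscle proteins. 1-RM is in neither list. A reader might infer that the primary strength analysis, or the effect sizes carried into the follow-up application, are compromised. The documents do not support that: the notes cover 1-RM only, and the sample-size section limits the effect-size purpose to primary and secondary outcomes. This objection stands.

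A reader might also infer that the baseline is simply a post-treatment value. That is too strong. The option is permissive, and a test before the first session, with no LPA yet done, is after randomisation but before training.

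The biopsy argument is weakened too. The 5-day minimum is there for recovery, only one leg is sampled, chest press should be unaffected, and all arms have the procedure. It gives a between-arm difference only if use of the option or its timing differs by arm, and nothing in the documents shows that it will. Nor do they say that test methods will differ within a subject; they only fail to rule it out.

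Finally, Screening Part II is not an ideal slot. Parts I and II are meant to share a day where possible. Part I includes a treadmill test to exhaustion, and Part II itself includes 120 maximal knee-extensor contractions. This stands, and the remedy has to allow for it.

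None of this removes the conflict of order. Two sections permit a baseline test after randomisation; another says that baseline testing comes first.

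**Conclusion.** The point holds in a limited form. The text allows a baseline 1-RM that is after randomisation, after biopsy and possibly after assigned exercise in amounts that differ by arm. This is a stated permission that contradicts the plan's own order, not merely a missing detail. It affects 1-RM as a supporting strength measure and leaves the primary analysis alone.

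Neither the size nor the sign of any bias can be derived from the documents. On the assumed ranges it runs from negligible to 0.30 SD between arms, well below the 1.14 SD yardstick, and opposing effects may partly cancel. A claim that gains will be inflated, or that arms will be biased against each other, would go beyond the evidence. The case for a change is that a cheap rule removes an ambiguity that could not be reliably corrected afterwards.

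**What to change.** Remove the first-week option for the baseline test from Screening Visit, Part II and from One-Repetition Maximum Testing. Require every baseline 1-RM before the V2 biopsy and before randomisation. It can stay at Screening Part II or, where same-day fatigue from the VO2 peak or endurance test is a concern, move to a separate short attendance at LSU. Keep the last-week option for the post-training test. Require the same method, true or submaximal, at both time points within a subject.

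If a first-week test cannot be avoided, do it before any assigned activity, including LPA breaks, record its date, and add a sensitivity analysis that excludes late baselines.

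The cost is a wording change, some loss of scheduling flexibility and, for some subjects, one extra short trip for a test of about 15 minutes.

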Although awareness of the detrimental impact that sedentary behavior has on skeletal muscle and cardiometabolic health has increased over the last 20 years, more than 60% of older adults remain sedentary for greater than 8 hours per day. Moreover, 80% to 90% of adults 60 years of age or older do not meet the current public health guidelines for aerobic exercise (AE) or resistance exercise (RE) based physical activity (PA). Collectively, these adverse health behaviors contribute to the development of multiple chronic medical conditions commonly afflicting older adults, including type 2 diabetes, cardiovascular disease, sarco/dynapenia, frailty, and premature mortality. Emerging evidence suggests that breaking up sedentary time with light intensity PA (LPA) improves muscle and cardiometabolic health. Recent data also suggest that RE combined with moderate intensity AE effectively improves muscle and cardiometabolic health in older adults. However, the impact that RE combined with LPA breaks in sedentary time has on muscle and cardiometabolic health in older adults remains unknown. The overall objective of this pilot study is to determine the effect of 16 weeks of RE alone or RE combined with LPA breaks in sedentary time on muscle and cardiometabolic health. The central hypothesis is that the addition of LPA breaks in sedentary time will enhance RE-induced improvements in muscle and cardiometabolic health in sedentary older adults. Our overall approach to test our central hypothesis is to recruit and study 36 physically inactive community dwelling older adults (65-80 years) who are randomized to 16 weeks of either (i) RE (2 x/wk), (ii) RE (2 x/wk) and LPA breaks in sedentary time (5 d/wk, 6x10 min breaks per day at 2 METS, ~500 kcal/wk above resting metabolism), or (iii) RE (2 x/wk) and moderate intensity AE (3 d/wk, 50 min/session at 4 METS, ~500 kcal/wk above resting metabolism). The effect that these PA interventions have on muscle health will be measured by changes in muscle strength, mass, and quality (strength/mass) using isokinetic dynamometry and dual-x-ray absorptiometry (DXA) (primary outcomes). In addition, improvements in muscle oxidative capacity will be measured using high-resolution respirometry and oxidative damage to muscle proteins by immunoblotting (secondary outcomes). The effect

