The LPA breaks in ST will consist of walking at ~2 METS for 6x10 min bouts, which will be completed throughout the day, with ~1 bout per hour. Alternative 2 MET mobility-based activities may also be provided using the Compendium of Physical Activities to promote adherence. We may use text/email messaging to send reminders, the "Stand Up! The Work Break Timer" (Apple/Android App) to promote adherence to the LPA breaks in ST protocol. We may also use the CentrePoint Cloud-Based Data Capture and Management Platform to send reminders to study participants. We will initially send these reminders on the days in which the subjects do not report for their RE sessions, the frequency of these reminders may be increased or decreased based on adherence. To reduce the risk of injury and muscle soreness, we will progressively increase the intensity and volume of the exercise prescriptions to the targeted training intensities over the first month of the intervention. Prior to each training session, we will assess resting blood pressures and heart rates. We will not allow subjects to exercise if they have a resting diastolic blood pressure > 100 mm Hg, resting systolic blood pressure > 180 mm Hg, or resting heart rate > 100 beats per min. We will also assess heart rates using heart rate monitors (e.g., Polar or Zephyr Bioharness) and ratings of perceived exertion (RPE, Borg 6-20) throughout the supervised exercise sessions. We will also measure the subjects' weight once per week during one of their scheduled exercise visits.

	Mon	Tue	Wed	Thu	Fri
A. Resistance Exercise (RE)		
 • Leg Press • Leg Extension • Leg Curls • Chest Press • Lat Pulldowns • Shoulder Press • Triceps Extension • Biceps Curls 
3 Sets 10-12 Reps to Failure
		
 • Leg Press • Leg Extension • Leg Curls • Chest Press • Lat Pulldowns • Shoulder Press • Triceps Extension • Biceps Curls 
3 Sets 10-12 Reps to Failure
	
B. LPA Breaks in Sedentary Time*	6x10 min bouts at 2 METS	6x10 min bouts at 2 METS	6x10 min bouts at 2 METS	6x10 min bouts at 2 METS	6x10 min bouts at 2 METS
C. Aerobic Exercise	1 x50 min bouts at 4 METS		1 x50 min bouts at 4 METS		1 x50 min bouts at 4 METS

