Table 2. The RE group will complete supervised RE (2x/wk) (A). The REALPA breaks in ST group will complete supervised RE (2x/wk) and regular unsupervised LPA breaks in ST (5x/wk) (A+B). The RE+AE group will complete supervised RE (2x/wk) and calorically matched moderate intensity AE (3x/wk) (A+C).

Physical Activity Monitoring During Intervention. To quantify total physical activity throughout the intervention, we will ask that subjects wear a physical activity monitor (Actigraph, GT9X) on their wrist 24 h/d for the duration of the study and a second physical activity monitor (Actigraph, GT9X) on their thigh during weeks 1, 4, 8, 12, and 16 for further quantification. We will screen raw data from these monitors for periods of valid wear-time with a required minimum wear-time of 10 h per valid wear-day and 4 valid wear-days per week.^{23,24} We will use standard algorithms to characterize the patterns of PA and ST.²⁵

Adherence Monitoring During Intervention. We will monitor each subject's attendance to the prescribed exercise training sessions and exercise training logs to assess adherence to the exercise intervention. We will also use the physical activity monitoring data to help assess adherence to the exercise intervention. De-identified physical activity monitoring data will be uploaded to the CentrePoint Cloud-Based Data Capture and Management Platform to facilitate data collection and monitoring.

Visit 3 (V3) (End of Exercise Intervention). During last week of the intervention (i.e., week 16), subjects will be asked to complete V3, with two parts. Part I will occur PBRC and Part II at the LSU Exercise Physiology Laboratory on the main campus of LSU.

V3, Part I (about 2 hours).

After an overnight fast (> 10 hours), subjects will report to PBRC to complete V3, Part I. During this visit, we will measure height, weight and vital signs. We will then perform the SPPB and Exercise Test (VO₂ Peak).

V3, Part II (about 1 hour).

Subjects will report to LSU Exercise Physiology Laboratory to complete V3, Part II (non-fasted). The visit procedures for this visit can be done at a regularly scheduled exercise session and would be completed prior to the start of that day's exercise. During this visit, we will conduct the Biodex, 1-RM, and Handgrip Strength and Endurance Testing.

Posttraining Visit 4 (V4) (About 5 hours).

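### The light-activity and aerobic add-ons match on nominal gross energy (10 MET-h/wk each) but not on the stated basis of energy above rest (about 5.0 versus 7.5 MET-h/wk)

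*Combined protocol and SAP*

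**What the plan says.** The opening summary gives the LPA add-on as "5 d/wk, 6x10 min breaks per day at 2 METS, ~500 kcal/wk above resting metabolism" and the AE add-on as "3 d/wk, 50 min/session at 4 METS, ~500 kcal/wk above resting metabolism". The same doses and energy figure return under Exercise Interventions in Screening and Study Visits, and again under Exercise Interventions in Risks to Human Subjects. Both of those sections describe the aerobic component as "calorically matched moderate intensity AE (3 d/wk, 50 min/session at 4 METS". The Table 2 legend repeats the label, "calorically matched moderate intensity AE (3x/wk) (A+C", without saying whether the match is gross or net of rest.

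The intensities are approximate. For the breaks the plan says "The LPA breaks in ST will consist of walking at ~2 METS for 6x10 min bouts". The treadmill walking is likewise about 4 METs. The two components also carry bands of roughly 30-40% and 60-75% of VO2 peak.

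On the role of the aerobic arm, the plan says "The RE+AE group serves as the standard of care". On body weight it says "We will also measure the subjects' weight once per week during one of their scheduled exercise visits", but nothing uses that weight to set the dose. For the activity monitors it says "We will use standard algorithms to characterize the patterns of PA and ST", and it names no conversion to energy. It gives no reference body weight and no MET-to-kcal factor.

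**The concern.** A MET value normally includes the resting rate. Halving the time while doubling the METs therefore keeps gross energy constant. It does not keep energy above rest constant, because the longer, gentler activity has more hours of rest subtracted from it. The plan states its match on the net basis, so the doses and the stated energy need to be checked against each other.

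What is at stake is the reading of the contrast between RE with LPA breaks (REALPA) and RE with AE (RE+AE). Study Endpoints lists between-group changes in body composition, glucose, lipids and glucose tolerance. If these two arms differ on such an outcome, the label invites the reading that energy was held equal and that pattern or intensity explains the difference. The doses may also be carried into the follow-up application that this pilot is meant to inform.

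**Working it through.** **Inputs from the plan** (main bouts only; RE is common to all arms; full dose after the first-month ramp)
- LPA: 5 d × 6 × 10 min = 300 min = 5.0 h/wk at 2 METs.
- AE: 3 × 50 min = 150 min = 2.5 h/wk at 4 METs.
- Stated energy: about 500 kcal/wk above rest for each.

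**Assumptions, not in the plan:** METs are multiples that include rest; rest = r METs, with r from 0.7 to 1; 1 kcal/kg/h per MET; body weight w of 60, 75 and 90 kg.

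**1. The plan's match.** Gross energy = hours × METs.
- LPA: 5.0 × 2 = 10 MET-h/wk.
- AE: 2.5 × 4 = 10 MET-h/wk.

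The match reproduces on gross energy.

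**2. The stated basis.** Net energy = hours × (METs − r). The gap is 2.5(4 − r) − 5(2 − r) = 2.5r, so AE is higher at any positive resting rate.

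| r | LPA net | AE net | AE ÷ LPA |
|---|---|---|---|
| 1.0 | 5.0 | 7.5 | 1.50 |
| 0.9 | 5.5 | 7.75 | 1.41 |
| 0.8 | 6.0 | 8.0 | 1.33 |
| 0.7 | 6.5 | 8.25 | 1.27 |

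**3. In kcal/wk, with r = 1.** LPA = 5w and AE = 7.5w.

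| Weight | LPA | AE | Gap |
|---|---|---|---|
| 60 kg | 300 | 450 | 150 |
| 75 kg | 375 | 563 | 188 |
| 90 kg | 450 | 675 | 225 |

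LPA reaches 500 at 500 ÷ 5 = 100 kg, and AE at 500 ÷ 7.5 = 66.7 kg. The weight with equal misses solves 12.5w = 1000, so w = 80 kg. There the doses are 400 and 600, each 20% from 500.

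**4. Can the approximate intensities restore a net match?** With r = 1 and intensities L and A, a match needs 5(L − 1) = 2.5(A − 1), so A = 2L − 1. The nominal pair fails: L = 2 would need A = 3, and A = 4 would need L = 2.5. If both are still to round to 2 and 4, L must lie between 2.25 and 2.5 and A between 3.5 and 4.

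One example is L = 2.3 and A = 3.6 at an assumed VO2 peak of 6 METs. These are 38% and 60% of peak, both inside the bands. Net energy is 5 × 1.3 = 6.5 and 2.5 × 2.6 = 6.5 MET-h/wk. At 77 kg each is 77 × 6.5 = about 500 kcal/wk.

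**5. Warm-up and cool-down.** Supervised sessions include these and the unsupervised breaks do not. Taking 5 minutes for each at an assumed 2 METs adds 3 × 10/60 × (2 − 1) = 0.5 MET-h/wk to AE, giving 8.0. This widens the gap.

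**The case against.** The strongest reply is that the plan marks its intensities as approximate and gives VO2 peak bands. A reader of the tables above might infer that a net figure of about 500 kcal cannot hold for both add-ons at any one body weight. The documents do not support that. Step 4 gives in-band intensities that match at about 500 kcal net at an ordinary weight. That part of the reply stands, and it confines the finding to the nominal 2 and 4 METs. It does not rescue the text, because the match then needs LPA above nominal with AE below it, and the plan prescribes no such offset.

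The second reply is that the label is true on gross energy, and the Table 2 legend attaches no net qualifier. This also stands. It would be too strong to call the label simply false. The conflict lies with the net-of-rest figure that accompanies it elsewhere.

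The third reply is that METs might be meant as above rest. Both add-ons would then be 10 MET-h/wk net, and the bands do not exclude it. But no text says so. The dose would be 600, 750 and 900 kcal/wk at 60, 75 and 90 kg, reaching 500 only at 50 kg, so the stated figure would still fail at ordinary weights.

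Finally, the harm is an inference that the plan does not itself draw. RE+AE is there as standard of care, and the central hypothesis concerns adding LPA to RE. Even a perfect net match would not isolate pattern or intensity, since AE is supervised and the breaks are not. All of this stands, and it is why the point is minor.

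**Conclusion.** Wrong as written; minor. At the nominal prescriptions the two add-ons are equal on gross energy and unequal on the net basis the plan states. The AE net dose is 50% higher at rest = 1 MET and 27% higher at rest = 0.7 MET. The shared figure of about 500 kcal/wk above rest therefore does not describe both add-ons at those intensities.

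The direction and the ratio do not depend on body weight. They rest on METs being multiples that include rest. The kcal values also rest on the assumed conversion and weights. Doses actually achieved will vary with adherence and with where each person falls in the bands.

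A reader might infer that the trial's main comparison or its size is compromised. It is not: REALPA versus RE does not rely on the match, and neither the tests nor the 12 per group use the energy figure.

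**What to change.** - In the opening summary and in both Exercise Interventions sections, remove the statement of about 500 kcal per week above rest for both add-ons.
- In both Exercise Interventions sections and the Table 2 legend, replace the calorically matched label with: matched on nominal gross energy (10 MET-h/wk each).
- State the nominal net doses: about 5.0 MET-h/wk for LPA and 7.5 MET-h/wk for AE, main bouts only, taking rest as 1 MET.
- Add one sentence: REALPA and RE+AE are not matched on energy above rest and also differ in supervision, so a difference between them cannot be attributed to activity pattern or intensity alone.

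The cost is wording in four places plus one sentence. The prescriptions, tests, sample size and the REALPA versus RE hypothesis stay as they are.
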